### **Participant Consent Procedures:**

Participants will have the option to complete the informed consent procedures either: In person at Boston Medical Center (BMC); In person at their home (2 research staff will travel to the participant's home); or remotely via videoconferencing or telephone with research staff. Paper copies of the adult consent form can be read and signed, or participants will be able to access an electronic version of these forms and can sign via REDCap. Research staff will conduct the informed consent process with the parent/guardian, which will include a detailed description of the eligibility determination, randomization, active intervention, control condition, and expectations for participation. Participants will be also told that they are free to take breaks and/or terminate the consent process or study visit at any time. Potential participants will be told that they do not have to answer any questions that they do not want to answer or that make them uncomfortable. Participants will be told that reports of research results will not specifically identify them. Participants will be informed that they will be compensated upon completion of baseline assessments (\$100) and also upon completion of follow-up assessments at 3, 6, and 12 months post baseline (additional \$100 per time point), but not for other study activities (including the clinical interview or intervention sessions). Signed consent will be obtained prior to collection of any research data. The consent form will detail a section on participant Right to Re-Contact. Participants can opt to participate in the study but not be re-contacted.

Participants completing the electronic REDCap form will provide an e-signature typing in their name and date, or drawing their signature on the screen (phone, computer, or tablet/iPad) with their finger, mouse, surface pen, etc. Parent or legal guardian consent will be required to participate in the study. Study staff members are trained in Boston University Medical Campus (BUMC) IRB policy and will closely follow consent procedures as outlined by the BUMC IRB. Potential subjects will be provided the consent document which details the background, purpose and procedures of the study. The study details will be reviewed with potential participants who will be given the opportunity to ask questions about the study and their participation. All participants will be given, mailed or emailed an unsigned copy of the consent form for their records. They may additionally be given, mailed or emailed a copy of their signed consent form, if requested.

If a participant indicates that they are interested in participating in the study, but cannot schedule a study visit to complete the informed consent procedures, or have previously missed their scheduled study visit, participants will have a period of 3 months to decide their participation and schedule a study visit. After the 3-month period, interested participants will be required to be re-screened as eligibility criteria may have changed. Research study staff will then re-administer the screening procedure to determine study eligibility.

As this study will enroll Spanish-speaking participants, the consent form will be translated into Spanish by the BMC interpreter services. The consenting process and interviews will be conducted in Spanish by fluent Spanish speakers or with the assistance of professional interpreters.

Participants can either read themselves or be read the consent form by a member of the research staff. After reviewing the consent form, all participants will be delivered the Assessment of Capacity, a teach-back process to ensure his/her understanding of the project, the purpose and procedures involved, and the voluntary nature of his/her participation. Those who have difficulty answering the items on the capacity questionnaire will have the study re-explained by research staff with a focus on aspects they did not understand. Those who demonstrate understanding of the study and voluntarily agree to participate will be asked to sign the Informed Consent Form.

### **Baseline Assessment**

If the caregiver consents to participate, they will proceed to complete the baseline assessments. Assessments can be completed at the same time as the informed consent, or at another time, at the convenience of the participant. All study assessments can occur in person at BMC, in person at the participant's house, or remotely through REDCap survey links, whichever is most convenient and appropriate for the patient. If needed, the interventionist can read the questions out loud to the parent and record their answers over Zoom or telephone. Participants will not be excluded if they cannot read and answer questionnaires themselves, nor will they be excluded if they do not have access to the necessary technology or internet required to complete surveys electronically. If participants are willing, research staff will read the questions and answer choices to them over the phone, Zoom, or in person, and make note of their responses in the study file. Participants who prefer to complete the surveys online will be sent REDCap survey links to their emails or mobile phone (through Twilio, a third party web service that enables REDCap for SMS text survey link distribution) following informed consent and will be encouraged to complete the baselines surveys within 48 hours of consent.

### **Randomization Procedures**

Once a caregiver gives consent to enroll in the study, they will be provided with a unique ID number and this ID number will be connected to their identifiable data (access to identifiable data will be limited to only research staff members and investigators listed on the IRB). Once consent and baseline assessment are completed, the caregiver/family will be randomized. Participants will be randomized to either the PRE-CARE intervention or to the care as usual control condition through the computerized randomization feature of REDCap. If a participating caregiver has multiple eligible children, they will be randomized by family. Randomization will be stratified by primary language (English and Spanish). Due to the nature of the intervention, we will not be able to blind study participants or research assistants serving as interventionists. Study assessments will be completed by parents independently, but if assistance is needed, it will be provided by a separate research staff member who is not the interventionist.

After the random assignment has been generated in REDCap, research staff will contact participants by phone to share their assignment, and with their permission, also inform the clinical care team of the study assignment. If a participant is randomized to the PRE-CARE intervention, research staff will then schedule their first study visit with the family. Research staff will aim to schedule this first study visit as soon as possible, preferably within one week of the date that the random assignment was generated. If a participant is randomized to care as usual, the parent will be advised to follow up with their clinical providers to determine the next steps for their child's treatment according to the standard of care at their clinical site. Clinical providers will also be advised that the family has been randomized to care as usual. Results of psychometric tools (i.e., CBCL 1.5-5 and ADHD-RS-IV-Preschool Version) will be shared with providers for all families with permission of the participating parent. Research staff will not contact the families in the control condition again until the time of follow-up assessments at 3, 6, and 12 months following completion of baseline assessments.

### **Study Intervention (PRE-CARE)**

Research staff will then ask participants to complete the PRE-CARE questionnaire prior to their scheduled study appointment. The preference is for participants to complete the PRE-CARE questionnaire electronically via a REDCap survey link. If a participant agrees to this and is comfortable with using the electronic survey technology, the RA will send them the link to the screener by email or text message. If the participant prefers to complete the questionnaire on paper, they can do so at the time of the first scheduled study visit. Lastly, if a participant has any difficulties with reading and/or would strongly prefer for the questionnaire to be administered verbally, the research staff will verbally ask the participant the PRE-CARE questions via phone or videoconference prior to the time of the first study visit. Research staff will note method of administration in our REDCap database. If participants have not completed the questionnaire prior to their study visit, interventionists will have them complete it at the beginning of their first intervention session.

Participants will be informed that the first study visit will last up to 60 minutes if necessary and acceptable to the participant. The first study visit will consist of the following: (1) parent self-report completion of the PRE-CARE social needs screener (if not already completed electronically in REDCap prior to the time of the study visit) and interventionist review of responses, (2) distribution of Family Resource Booklet, with areas of specified need highlighted; and (3) targeted resource navigation. The study intervention is described in detail in the "study intervention" section of this application.

### **Control Intervention ("Care as usual")**

Families randomly assigned to the control condition will continue to receive care as usual, which in the Boston Medical Center system includes screening for social needs annually at well-child visits as recommended by the American Academy of Pediatrics, followed by provision of information as needed by the family. Families will also be offered the opportunity to make research assessments available to their primary care physician for best continuity of care.

### Parent-Reported Study Assessments

In addition to the baseline assessments, all 60 participants (30 intervention and 30 control) will complete follow-up assessments at 3, 6, and 12 months following the completion of baseline assessments. Follow-up assessments can be completed in person at the research office, in the participant's home, or remotely by phone or videoconference.

Participants in the intervention arm only will also be invited to participate in an in-depth exit interview once their intervention period is complete in order to collect feedback on the intervention content and strategy and explore putative intervention mechanisms. If participants refuse to participate in the exit interview, but complete the survey assessments, they will still be compensated.

At any of the assessment timepoints, if participants refuse to complete select questions in the assessments, but answer most questions, they will still be compensated.

It is anticipated that in some cases, two primary caregivers will desire to be part of the intervention. Other adult family members involved in primary caregiving may also participate in any intervention sessions as long as the consenting primary caregiver is present for all sessions and is the only one completing all intervention assessments.

At baseline, participants will complete a Contact Information form that details their preferred mode of contact for completion of follow-up assessment (email, phone, mail). At each subsequent time point, RAs will refer to the contact information form and send reminders (via email, phone, or text message, based on preference) to the participant to complete their follow-up assessments every 4 days for at least 2 weeks (or until the assessment is complete). RAs will run weekly reports off REDCap to see which participants have not completed their assessments. If a participant has not completed their assessment after 2 weeks, the RA will call the participant to complete the assessment over the phone. At each of the follow-up timepoints (3, 6, and 12-months after baseline), RAs should stop reminder calls to participants 8 weeks after the participant was initially contacted to complete the assessment.

### Research Staff-collected Process Outcomes

Research staff will collect and analyze process measures throughout the intervention period in order to optimize intervention delivery. They will record:

- 1) **Contacts:** Each contact with a parent/guardian (intervention or control) including the date, time, person who initiated contact, length of time per contact, and modality of contact (e.g. phone, zoom, in person);
- 2) **Referrals made** (including agencies, date of referral, and parent/guardian vs. staff referral)
- 3) **Resources accessed** (including specific resource accessed, resource category, date accessed)
- 4) **Needs resolved** (date at which a participant indicates they no longer need help with a need and why, e.g. they received help or they no longer need help or needed help does not exist)

Throughout the study, research staff will also maintain a record (counts only) of the number of:

- 1) Potential participants identified, by which recruitment strategy, and from which clinic;

- 2) Potential participants screened ineligible;
- 3) Potential participants eligible but refusing participation;
- 4) Participants dropping intervention before its end with reason if known;
- 5) Participants dropping out of the study before its end with reason if known.

### **Electronic Medical Record**

Additionally, charts of the children whose parents/guardians are participating will be accessed in order to collect utilization data directly from their electronic medical records (EMRs) including the following data for each child whose parent has participated (intervention and controls):

- 1) Number of medical encounters, encounter providers, and diagnoses during the intervention period
- 2) Prescribed medication prior to and during the intervention period
- 3) Other diagnoses in the medical record
- 4) Documented referrals to other specialty services or community agencies and referring provider

### **Safety Assessment**

If study staff learn of any acute safety concerns, such as current thoughts about suicide, self-harm, or intent to harm others, abuse, neglect, or other reportable conditions, research study staff will interrupt study activities and utilize the Safety Assessment form to assess parent or child risk. Research staff will probe participants about frequency and severity of the concern to identify participants and their child who may be at immediate risk and require further intervention. Upon completion of the Safety Assessment, research staff will contact the study PI who will conduct a brief acute safety assessment over the phone, zoom, or in person. PI will then utilize clinical judgment to determine further course of action.

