### 10.4 Stopping Rules

Study contacts will be stopped if there is an acute and immediate concern for the safety of a parent or child. This would include the revelation of current abuse, neglect, suicidal or homicidal ideation. In addition, participants may choose to withdraw from the study at any point and for any reason.

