If the study staff learns of any acute safety concerns, such as current thoughts about suicide, self-harm, or intent to harm others, abuse, neglect, or other reportable conditions, investigators may need to break confidentiality to prevent this harm from happening. Participants are made aware of this during the consenting process. Study staff will abort study procedures and take the necessary steps to keep the participant and child from harm. The study Principal Investigator will be immediately notified by pager. Children or parents may be referred for emergency evaluation at the Boston Medical Center Psychiatric Emergency Services or at the Boston Emergency Services Team (BEST) located near the hospital. We also may contact treating health care providers to be sure they are aware of the risk identified. In addition, if research staff identify any concern for current abuse or neglect, they will page the study investigator who must report this to the Department of Children and Families.

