## 15 Appendix

### Schedule of Events

Domain/measure	Informant	Assessment Time Point (Month)			Intervention Period (0-3+ months)
		0	3 (Post-intervention)	6	
Family Background					
Background Socio-demographic Questionnaire	Parent	X			
Unmet Social Needs Questionnaire and Adequacy of Resources	Parent	X	X	X	X
Child Symptoms, Adverse Experiences, and Treatment Utilization					
Child Behavior Checklist 1.5-5	Parent	X		X	X
ADHD Rating Scale, Version IV (ADHD-RS-IV), Preschool Version	Parent	X	X	X	X
CYW Adverse Childhood Experiences Questionnaire (ACE-Q) Child	Parent	X			X
Parent Symptoms, Activation and Treatment Utilization					
Patient Health Questionnaire (PHQ-9)	Parent	X	X	X	X

Adult ADHD Self Report Scale (ASRS-v1.1)	Parent	X	X	X	X
Perceived Stress Scale (PSS)	Parent	X	X	X	X
Parenting Stress Index-Short Form (PSI-SF)	Parent	X	X	X	X
Intervention Feasibility, Acceptability, and Content					
PRE-CARE Exit Interview – PRE-CARE condition only	IE (via Parent)		X		
PRE-CARE Feasibility and Acceptability Form - PRE-CARE condition only	Parent		X		
Interventionist Post-Session Summary Form - PRE-CARE condition only	RA	X	X		
Premature Termination Form	RA	X	X

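### The acute-safety steps start only once staff know of a concern, and the plan gives a PHQ-9 answered alone online no stated route to that point

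*Combined protocol and SAP*

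**What the plan says.** The acute steps appear in two places with the same trigger. Section 9, Safety Assessment, begins "If study staff learn of any acute safety concerns, such as current thoughts about suicide, self-harm, or intent to harm others". Section 11.1 begins "If the study staff learns of any acute safety concerns". Once that condition is met the plan is specific: study activities stop, staff complete the Safety Assessment form, the PI is paged and assesses the risk, and emergency evaluation is available. Section 10.4 adds: "Study contacts will be stopped if there is an acute and immediate concern for the safety of a parent or child".

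The PHQ-9 is a secondary outcome (Section 4.2.1). Its row in the Schedule of Events carries four marks, which fit the four assessments named in the Protocol Summary: baseline and months 3, 6 and 12. On how forms are completed, Section 9 says under Baseline Assessment: "Participants who prefer to complete the surveys online will be sent REDCap survey links to their emails or mobile phone". Under Randomization Procedures it says: "Study assessments will be completed by parents independently". Help, if needed, comes from a staff member other than the interventionist.

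For control families, Randomization Procedures states: "Research staff will not contact the families in the control condition again until the time of follow-up assessments at 3, 6, and 12 months". Section 5 likewise rules out contact begun by research staff between questionnaires.

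**The concern.** A trigger that depends on staff knowing works for something said to staff in a call or visit. It does not work by itself for an answer typed into a web form with nobody present. A step is needed between submission and staff awareness: someone who looks, or an alert that makes them look. If the plan is followed as written, a parent who reports thoughts of self-harm online prompts no one until the record happens to be opened, and no time is set for that.

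At stake is the safety of parents whom the study itself asks about depression up to four times. The point applies in both arms. In the control arm it is compounded, because the contact rule states no exception for a worrying answer.

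**Working it through.** The plan states no figure on this point, so the check is mainly of text. Each place that could carry an online PHQ-9 answer to staff was read in turn.

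| Place | What it provides | Does it carry a PHQ-9 answer to staff? |
|---|---|---|
| Section 9, Safety Assessment; Section 11.1 | Action once a concern is known | No; it starts after that point |
| Section 10.4 | Stops contacts on an acute concern | No; the concern must already be known |
| Section 9, Parent-Reported Study Assessments | Weekly REDCap report of who has not completed | No; it looks at completion, and a submitted form drops off the list |
| Section 11.1, on REDCap | Data available to the investigator at once, for statistical analysis | Access exists; no safety review is assigned |
| Section 11.2 | Real-time monitoring listed as a REDCap capability | A software feature, not an assigned task |
| Section 9, Removal of Participants | Clinical assessment if a parent reports worsening mental health | Names no PHQ-9 reader, answer or time limit |
| Section 9, Randomization Procedures | "Results of psychometric tools (i.e., CBCL 1.5-5 and ADHD-RS-IV-Preschool Version) will be shared with providers", with permission | The PHQ-9 is not among the named tools |
| Section 9, Control Intervention | Offer to make research assessments available to the primary care physician | Optional, with no timing |
| Sections 5 and 10.2 | Refer to a separate safety protocol | Not supplied; it may cover this |

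No row names a reader, a time limit or a triggering answer.

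The number of forms involved:

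- Inputs: 60 parents, 30 per arm (Section 9, Parent-Reported Study Assessments); 4 PHQ-9 time points (Schedule of Events); 25% attrition (Section 12.2).
- Planned forms: 60 × 4 = 240, or 30 × 4 = 120 per arm.
- If all attrition fell before month 3 (an assumption): 60 × 0.75 = 45 parents remain, giving 60 + 45 × 3 = 195 forms.
- Follow-up forms only: 60 × 3 = 180, or 45 × 3 = 135 with that attrition.
- Share completed alone online: not given, so anywhere from 0% to 100%. The number of exposed forms therefore lies between 0 and 240.

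The number of positive answers cannot be derived from the documents.

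**The case against.** The strongest reply is that the rule may exist elsewhere. Section 10.2 says a detailed safety protocol is in place for mental health emergencies, and Section 5 applies a safety protocol to control families too. Neither that protocol nor the Safety Assessment form is supplied. This stands as a limit: the finding is that the rule is absent from this document, not that the study has none. It does not remove the point. Section 10.2 undertakes to check that the safety procedures work once activated, and an unread answer would never activate them.

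Several other replies are partly right. Forms read aloud by staff are heard at once. Follow-up may be done in person, by phone or by videoconference, and a form still missing after two weeks leads to a call. After baseline, every family is phoned with its assignment, though nothing says the answers are read first. The Safety Assessment text names suicidal thoughts and self-harm as concerns and does not exclude written answers; only the link to a questionnaire item is missing. These replies narrow the gap to forms completed without staff, chiefly at follow-up.

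Two stronger readings are tempting and are not supported. A reader might infer from the intervals between control-arm assessments that an answer would lie unread for months. Those intervals describe contact, not reading: the data can be seen at once, and the reading delay is simply unstated. A reader might also infer that adverse events will be under-detected in the control arm. Any such imbalance would come from the fortnightly navigation meetings in PRE-CARE. It is a separate matter that a PHQ-9 alert would not cure.

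**Conclusion.** The point holds in a limited form. The stated trigger is passive, a parent may answer the PHQ-9 alone online, and no supplied text provides for those answers to be looked at for safety. This is more than a missing detail, because a REDCap alert feeding the existing paging route is a cheap and safer method in both arms.

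Its size is at most 240 planned forms, with an unknown share completed alone online and an unknown, possibly zero, number of positive answers. A reader might want an expected count of self-harm responses, but the documents give neither a response rate nor an online share to support one.

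The conclusion assumes that the unseen safety protocol does not already set a review rule. Its importance also assumes that the standard PHQ-9 with its self-harm item is used, since the items are not printed.

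**What to change.** Add to Section 9, Safety Assessment, wording such as:

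> A positive answer on the PHQ-9 self-harm item counts as a concern that staff have learned of. Online submission of such an answer triggers an automatic REDCap alert to the PI through the existing paging route, and the Safety Assessment follows the same or the next day. PHQ-9 forms completed on paper or with staff are checked before the contact ends. This applies in both arms and is a safety exception to the rule against staff-initiated contact with control families.

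The time limit is an example; the team should choose one it can keep and write down which responses count as positive. If the safety protocol already contains such a rule, it is enough to cite it here and state its time limit.

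The cost is one alert rule, a small number of safety calls (number unknown, possibly none), some of them to control families, and an IRB amendment. No visit or questionnaire is added.
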